5.4.16. Disease-Specific Quality of Life at 30 Day Visit – PEmb-QoL

The PEmb-QoL at 30 days visit will be analyzed as with the following null and alternative hypotheses:

$H_0: \mu_{PQF} \geq \mu_{PQC}$ versus $H_A: \mu_{PQF} < \mu_{PQC}$

where μ_{PQF} represents the mean PEmb-QoL score at 30 day visit in the FlowTriever System group, and μ_{PQC} represents the mean PEmb-QoL score at 30 day visit in the CDT group. The hypothesis will be tested using a Wilcoxon Rank Sum test.

PROPRIETARY AND CONFIDENTIAL

The information contained in this document is the sole property of Inari Medical

	PEERLESS Study: Statistical Analysis Plan	Version 5.0 March 22, 2024 Page 23 of 25
---	--	--

5.4.17. General Health-Related Quality of Life at 30 Day Visit – EQ-5D-5L

The EQ-5D-5L at 30 days visit will be analyzed as with the following null and alternative hypotheses:

$$H_0: \mu_{EQF} \leq \mu_{EQC} \text{ versus } H_A: \mu_{EQF} > \mu_{EQC}$$

where μ_{EQF} represents the mean EQ-5D-5L score at 30 day visit in the FlowTriever System group, and μ_{EQC} represents the mean EQ-5D-5L score at 30 day visit in the CDT group. The hypothesis will be tested using a Wilcoxon Rank Sum test.

The secondary endpoints listed in this section will be assessed for patients in ITT and PP populations with descriptive statistics and hypothesis testing. Continuous variables will report any combination of mean, SD, median, Q1, Q3, IQR, minimum and maximum, while the categorical variables will report frequency count and percentages (%).

5.5. Exploratory Analysis

Exploratory analysis may be, but not limited to, performed on additional outcomes of interest with descriptive statistics and hypothesis testing. The same approach described in Section 5.6 will be applied to control for overall α . Continuous variables will report any combination of mean, SD, median, Q1, Q3, IQR, minimum and maximum, while the categorical variables will report frequency count and percentages (%).

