5.1. Sample Size

By assuming an 80% power with one-sided alpha of 2.5%, the win ratio methodology is applied to the primary endpoint that consists of five components. The required sample size is 432 subjects (216 subjects per arm); and planning for follow up attrition and further describing secondary endpoints/exploratory analysis, the study will enroll up to a total of 550 randomized subjects (RCT Cohort). The "event" proportions of the five components are based on Inari sponsored studies and a review of literature.

Up to 150 additional subjects who meet all eligibility criteria and who have an absolute contraindication to thrombolytics, whose initial planned primary treatment strategy includes FlowTriever, will be enrolled as part of the Contraindication Cohort. The same clinical assessments and follow up schedule will be administered in this cohort as is described for the RCT Cohort.

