5.6. Controlling for Multiplicity

For the primary and secondary endpoints related to safety, α is set to 0.05, to conservatively include all potential safety signals. The secondary endpoints listed below are considered as safety endpoints:

- Composite clinical endpoint constructed as a win ratio hierarchy of the following four components, assessed at hospital discharge or at 7 days after the index procedure, whichever is sooner:
 - All-cause mortality, or
 - Intracranial hemorrhage (ICH), or
 - Major bleeding per ISTH³ definition, or
 - Clinical deterioration defined by hemodynamic or respiratory worsening, and/or escalation to a bailout therapy
- Four Individual components of the win ratio composite endpoint, assessed at hospital discharge or at 7 days after the index procedure, whichever is sooner:
 - All-cause mortality
 - Intracranial hemorrhage (ICH)
 - Major bleeding per ISTH³ definition

PROPRIETARY AND CONFIDENTIAL

The information contained in this document is the sole property of Inari Medical

	PEERLESS Study: Statistical Analysis Plan	Version 5.0 March 22, 2024 Page 24 of 25
---	--	--

- Clinical deterioration defined by hemodynamic or respiratory worsening, and/or escalation to a bailout therapy
- All-cause mortality within 30 days from index procedure
- PE-related and all-cause readmission within 30 days from index procedure
- Device and drug-related serious adverse events through the 30 day visit
- Clinically Relevant Non-Major (CRNM) and Minor bleeding events through hospital discharge or at 7 days after the index procedure, whichever is sooner

For the secondary endpoints not related to safety, the family-wide type I error rate will be controlled at one-sided $\alpha=0.025$ using the Bonferroni correction with an effective number of independent tests. The typical Bonferroni correction assumes all tests are independent and is therefore extremely conservative. An alternative approach to estimate the effective number of independent tests for the correlated tests has been proposed by Gao et al (2008)⁹. Therefore, the α to adjust for multiplicity is simply

$$\frac{\text{familywide type I error}}{\text{effective number of independent tests}}$$

The secondary endpoints listed below are considered as non-safety endpoints:

- ICU admission and ICU length of stay post index procedure and following the index procedure
- Change in right-ventricular/left-ventricular (RV/LV) ratio from baseline to 24 hour visit, as measured by echocardiography or CT

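### SAP 5.5 promises control of overall α across open-ended exploratory tests, but the 5.6 scheme controls only the seven non-safety secondaries and ties no secondary claim to the primary

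*SAP*

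**What the plan says.** SAP 5.5 allows exploratory analyses, including hypothesis tests, on additional outcomes that it neither lists nor caps. It adds: "The same approach described in Section 5.6 will be applied to control for overall" α. It does not say whether these tests join an existing family or form their own.

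SAP 5.6 contains two rules:

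- **Primary and safety secondaries.** "For the primary and secondary endpoints related to safety, α is set to 0.05, to conservatively include all potential safety signals". No sidedness is given and there is no adjustment across tests.
- **Non-safety secondaries.** "For the secondary endpoints not related to safety, the family-wide type I error rate will be controlled at one-sided" 0.025, by a Bonferroni correction whose divisor is an estimated effective number of tests. The members are then listed.

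SAP 5.1 sets the design alpha: "By assuming an 80% power with one-sided alpha of 2.5%, the win ratio methodology is applied to the primary endpoint". SAP 5.2 says that the primary and secondary endpoints all lead to hypothesis tests. SAP 5.4 writes directional hypotheses favouring FlowTriever for the secondaries, including the safety ones. Neither the SAP nor Protocol section 10 states an order of testing or makes secondary claims conditional on the primary.

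**The concern.** A reader of 5.5 would take it that the multiplicity scheme limits false claims over everything tested: primary, secondary and exploratory. The scheme it points to limits them in one family only. The primary spends its own alpha, the non-safety family spends a further 0.025 whether or not the primary succeeds, and each safety secondary is tested at an unadjusted 0.05. Adding exploratory tests under the same approach cannot produce overall control that 5.6 does not have.

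The stake is what may be claimed. As written, secondaries can be declared significant after a failed primary, and an exploratory result can be presented as alpha-controlled. In an open-label trial with one-sided superiority hypotheses on nearly every secondary, such statements will be read as confirmed benefits.

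**Working it through.** **Inputs**

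- Primary: one-sided 0.025 (SAP 5.1). This assumes that the 0.05 in 5.6 is two-sided. The critical value is then 1.960 either way.
- Non-safety family: one-sided 0.025 (SAP 5.6), seven tests (SAP 5.4.7 and 5.4.12 to 5.4.17).
- Safety secondaries: ten with a test (SAP 5.4.1 to 5.4.6 and 5.4.8 to 5.4.11). Device- and drug-related serious adverse events are listed as safety in 5.6 but have no test in 5.4. Counting them gives 11 or 12.
- My assumptions: divisor 7 for the non-safety family (the SAP gives no number), a common correlation of 0 to 0.7, all null hypotheses true, and one analysis set. The SAP tests both ITT and PP; that is not counted here.

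**The plan's own figure.** Seven tests at 0.025/7 = 0.00357 each sum to 0.025. The stated family-wide rate for the non-safety secondaries is reproduced for a fixed list of seven.

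**Primary plus non-safety family, no gate**

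- Independent tests: 1 − 0.975 × (1 − 0.025/7)^7 = 1 − 0.975 × 0.9753 = 0.049.
- Upper bound by summing: 0.025 + 0.025 = 0.050.
- If the primary's 0.05 were one-sided: 1 − 0.95 × 0.975 = 0.074.

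**With a gate.** If the primary null is true, no secondary can be claimed unless the primary has already been falsely rejected, so the error is at most 0.025. If the primary effect is real, the seven tests at 0.025/7 still hold their own family to 0.025.

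**Adding one separate exploratory family at 0.025.** 1 − 0.975^3 = 0.073 (sum 0.075), however many outcomes share that family.

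**Safety secondaries alone, ten independent tests**

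- At one-sided 0.025 (0.05 read as two-sided): 1 − 0.975^10 = 0.224.
- At 0.05: 1 − 0.95^10 = 0.401.

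**Effect of correlation** (simulated equicorrelated normal test statistics; the independent column is calculated):

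| Tests counted | Independent | 0.3 | 0.5 | 0.7 |
|---|---|---|---|---|
| Primary + non-safety family | 4.9% | 4.5% | 4.0% | 3.3% |
| + ten safety tests at 0.025 | 26.2% | 20.0% | 15.8% | 11.4% |
| + ten safety tests at 0.05 | 43.1% | 32.1% | 25.5% | 18.9% |

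The safety rows are indicative and probably high. The safety endpoints overlap: the four-event composite contains its components, and early deaths also count at 30 days. Fisher's exact test is also conservative for rare events.

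**If exploratory outcomes were pooled with the seven** (each counted as a full test). The threshold would be 0.025/7 = 0.0036 with none added, 0.025/12 = 0.0021 with five and 0.025/17 = 0.0015 with ten. A secondary with 80% power at 0.0036 would have 74.7% and 71.2%. If they are not pooled, the threshold stays at 0.0036.

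**The case against.** The strongest reply is that 5.6 never promises trial-wide control. It promises family-wide control for the non-safety secondaries, and if overall α in 5.5 means only the alpha of the family being adjusted, a single exploratory family at 0.025 satisfies it. A gate is then a design preference, and 4.9% is being held against a 2.5% limit that the SAP does not set. This stands in part. The trial-wide standard comes from the wording of 5.5, not from 5.6. But 5.5 does not define the term, and it does not say which of 5.6's two rules applies. Under the safety rule, exploratory tests would have no adjustment at all.

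The safety tests also have a stated reason: 5.6 leaves them unadjusted so as not to miss signals. That is sensible for detecting harm. It does not fit the hypotheses in 5.4, which test for superiority of FlowTriever.

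Three stronger conclusions might be inferred, and the documents do not support them:

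- **That the threshold for the seven secondaries falls as exploratory outcomes are added.** This happens only if they are pooled. Section 5.6 gives a closed list ("The secondary endpoints listed below are considered as non-safety endpoints"), and 5.5 does not say that anything is added to it. Pooling would in any case make the secondary tests stricter, not more error-prone.
- **That every exploratory outcome spends another 0.025.** A separate family shares one 0.025, and more outcomes tighten its per-test threshold.
- **That the primary result is compromised.** The missing gate does not alter the primary's own type I error.

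**Conclusion.** The concern holds in this form: the control of overall α stated in 5.5 is not delivered by 5.6, because 5.6 protects one family, leaves the primary and the safety secondaries outside it, and sets no order. For the primary plus the non-safety family the excess is modest: 4.9% if independent and 3.3% at correlation 0.7, against 2.5% with a gate. One separate exploratory family takes the independent figure to about 7.3%. The unadjusted safety secondaries are the largest source, at 22% to 40% alone for ten independent tests, and less with correlation.

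These figures rest on all nulls being true, a divisor of seven, and the primary at one-sided 0.025. If 5.6 means a one-sided 0.05 for the primary, 4.9% becomes 7.4%. The consequence is limited to secondary and exploratory claims. It should be corrected, but it does not threaten the primary conclusion.

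**What to change.** Make three changes to the SAP:

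1. In 5.5, replace the sentence on controlling α with: *Exploratory p-values are nominal, belong to no alpha family and support no claim.*
2. In 5.6, add: *The listed non-safety secondary endpoints are tested confirmatorily only if the primary F-S test is significant at one-sided 0.025.* This also settles the level and sidedness for the primary.
3. In 5.6, add: *P-values for the safety secondary endpoints are unadjusted, serve signal detection and support no confirmatory superiority claim.*

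Error over all confirmatory claims is then at most one-sided 0.025, provided that the divisor for the seven tests is valid. No data collection, sample size or procedure changes. The cost is in what can be claimed: no confirmatory secondary claim if the primary fails, and no significance claim for exploratory or safety-secondary results, including the four-component win ratio.

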5.6. Controlling for Multiplicity

For the primary and secondary endpoints related to safety, α is set to 0.05, to conservatively include all potential safety signals. The secondary endpoints listed below are considered as safety endpoints:

- Composite clinical endpoint constructed as a win ratio hierarchy of the following four components, assessed at hospital discharge or at 7 days after the index procedure, whichever is sooner:
 - All-cause mortality, or
 - Intracranial hemorrhage (ICH), or
 - Major bleeding per ISTH³ definition, or
 - Clinical deterioration defined by hemodynamic or respiratory worsening, and/or escalation to a bailout therapy
- Four Individual components of the win ratio composite endpoint, assessed at hospital discharge or at 7 days after the index procedure, whichever is sooner:
 - All-cause mortality
 - Intracranial hemorrhage (ICH)
 - Major bleeding per ISTH³ definition

PROPRIETARY AND CONFIDENTIAL

The information contained in this document is the sole property of Inari Medical

	PEERLESS Study: Statistical Analysis Plan	Version 5.0 March 22, 2024 Page 24 of 25
---	--	--

- Clinical deterioration defined by hemodynamic or respiratory worsening, and/or escalation to a bailout therapy
- All-cause mortality within 30 days from index procedure
- PE-related and all-cause readmission within 30 days from index procedure
- Device and drug-related serious adverse events through the 30 day visit
- Clinically Relevant Non-Major (CRNM) and Minor bleeding events through hospital discharge or at 7 days after the index procedure, whichever is sooner

For the secondary endpoints not related to safety, the family-wide type I error rate will be controlled at one-sided $\alpha=0.025$ using the Bonferroni correction with an effective number of independent tests. The typical Bonferroni correction assumes all tests are independent and is therefore extremely conservative. An alternative approach to estimate the effective number of independent tests for the correlated tests has been proposed by Gao et al (2008)⁹. Therefore, the α to adjust for multiplicity is simply

$$\frac{\text{familywide type I error}}{\text{effective number of independent tests}}$$

The secondary endpoints listed below are considered as non-safety endpoints:

- ICU admission and ICU length of stay post index procedure and following the index procedure
- Change in right-ventricular/left-ventricular (RV/LV) ratio from baseline to 24 hour visit, as measured by echocardiography or CT
- mMRC Dyspnea score at 24 hour visit and 30 day visit
- Length of post-index-procedure hospital stay (to a maximum of 30 days)
- Disease-specific and general health-related quality of life at the 30 day visit (PEmb-QoL and EQ-5D-5L)

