10. STATISTICS & DATA ANALYSIS

SAMPLE SIZE

By assuming an 80% power with one-sided alpha of 2.5%, the win ratio methodology is applied to the primary endpoint that consists of five components. The required sample size is 432 subjects (216 subjects per arm); and planning for follow up attrition and further describing secondary endpoints/exploratory analysis, the study will enroll up to a total of 550 randomized subjects (RCT Cohort). The sample size assumptions are based on Inari sponsored studies and a review of literature.

Up to 150 additional subjects who meet all eligibility criteria and who have an absolute contraindication to thrombolytics, whose initial planned primary treatment strategy includes FlowTriever, will be enrolled as part of the Contraindication Cohort. The same clinical assessments and follow up schedule will be administered in this cohort as is described for the RCT Cohort. The Contraindication cohort data will not be used for any PEERLESS protocol-defined hypothesis testing nor used to calculate any primary or secondary endpoints.

STATISTICAL METHODOLOGY

The statistical design objective for this trial is to compare the clinical outcomes of the FlowTriever System versus Catheter-Directed Thrombolysis (CDT) for use in the treatment of acute pulmonary embolism (PE). Since the primary endpoint is a composite clinical endpoint, a modified generalized Wilcoxon test (F-S test) proposed by Finkelstein & Schoenfeld⁷³ will be applied to examine the performance differences between the two treatment arms.

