5.2. Statistical Methodology

[figure not shown]
The statistical design objective for this trial is to compare the clinical outcomes of the FlowTriever System versus CDT for use in the treatment of acute pulmonary embolism (PE). Since the primary endpoint is a composite clinical endpoint, a modified generalized Wilcoxon test (F-S test) proposed by Finkelstein & Schoenfeld⁴ will be applied to examine the performance differences between the two treatment arms.

In this trial, the primary endpoint is a hierarchy of five clinical outcome components. Each subject in the study will be compared to each of the other subjects in a pairwise manner, regardless of which treatment arm the compared subject is in, and assigned a score, u_{ij} , of 1, -1, or 0, depending on whether the comparison has a favorable, unfavorable, or unsettled outcome in the hierarchy of the clinical events; i is the index subject to be compared with all other subjects in a pairwise fashion and j represents j^{th} subject comparison. For example, if a subject i is alive while a subject j died, the score is 1; if a subject i died while subject j is alive, the score is -1. If both subjects are alive/dead or any subject is missing in mortality status (i.e., a pair is unsettled/not comparable for the first outcome), the second clinical outcome (Intracranial hemorrhage) is compared and assigned a score of 1, -1, or unsettled in a similar comparison logic. Subsequently, within each pairwise comparison, the score is determined by comparing five clinical outcomes sequentially in the order of outcome priorities (see Figure 2). In summary, for each pair of subjects (i, j) , the score is defined as

$$u_{ij} = \begin{cases} 1, & \text{if subject } i \text{ does better than subject } j \\ -1, & \text{if subject } j \text{ does better than subject } i \\ 0, & \text{if it cannot be determined} \end{cases}$$

PROPRIETARY AND CONFIDENTIAL

The information contained in this document is the sole property of Inari Medical

Figure 2 Pairwise Comparison Flowchart

Finkelstein & Schoenfeld⁴ (F-S) then assigned a score $U_i = \sum_{i \neq j} u_{ij}$ to each subject i . Their proposed test is a score test based on the sum of the ranks for the treated group (see the following equation).

$$T = \sum_{i=1}^N U_i D_i$$

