where $D_i = 1$ for subjects in FlowTriever arm and $D_i = 0$ for subjects in CDT arm, and N is the number of total subjects in the trial. The proposed F-S statistic for the hypothesis of interest is T / \sqrt{V} , where $V = \frac{n_{FT} n_{CDT}}{N(N-1)} \sum_i U_i^2$ is the variance of T , n_{FT} and n_{CDT} are the number of subjects in FlowTriever and CDT

PROPRIETARY AND CONFIDENTIAL

The information contained in this document is the sole property of Inari Medical

	PEERLESS Study: Statistical Analysis Plan	Version 5.0 March 22, 2024 Page 17 of 25
---	--	--

arms, respectively, and $n_{FT} + n_{CDT} = N$. The hypothesis is tested by comparing the F-S statistic to the standard normal distribution (Finkelstein & Schoenfeld⁴).

To determine the sample size required to achieve 80% power given one-sided alpha of 2.5%, we first will simulate subject level data per data replicate. For a data replicate and within a treatment arm, clinical outcomes with event proportions are sampled from binomial distribution; ICU is from a multinomial distribution with 3 categories, including no ICU admission, ≤ 24 hours, and > 24 hours. We will assume each of the clinical outcomes are independent of each other. For example, we may sample 100 subjects per treatment arm, and within each treatment arm each has different clinical outcome proportions or means. Once we generate 200 subjects in total (100 per treatment arm), we may derive the F-S test statistic and its p-value. We will then repeat the process for 2,500 data replicates and derive 2,500 p-values based on F-S test statistics; power is the proportion of p-values that are ≤ 0.05 . Each given sample size number will thus lead to one power number to be calculated. As we alter the sample sizes in the simulation scenario, we can conduct a grid search to determine the minimal sample size required to achieve at least 80% power.

The primary and secondary endpoints will be analyzed for both ITT and PP populations, separately. Primary endpoint and secondary endpoints will lead to hypothesis testing whereas, only descriptive summary statistics will be provided for the Contraindication Cohort.

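### SAP 5.6 gives the primary and the safety secondaries an alpha of 0.05 without saying one- or two-sided, beside one-sided hypotheses and a design alpha of one-sided 2.5%

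*SAP*

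**What the plan says.** **Sizing.** SAP 5.1 reads "By assuming an 80% power with one-sided alpha of 2.5%, the win ratio methodology is applied to the primary endpoint", which has five components, and arrives at 432 subjects (216 per arm), with up to 550 randomized. Protocol section 10 opens its sample-size text the same way: "By assuming an 80% power with one-sided alpha of 2.5"%.

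**Simulation.** SAP 5.2 begins "To determine the sample size required to achieve 80% power given one-sided alpha of 2.5"% and then says "power is the proportion of p-values that are" at or below 0.05. The tail of those p-values is not given. Protocol section 10 has the same sentence.

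**Primary test.** SAP 5.3 states a one-sided hypothesis, with the alternative that FlowTriever has more winners than CDT, and gives no alpha. SAP 5.2 refers the F-S statistic to the standard normal without naming a tail. The win ratio gets a 95% bootstrap interval from the 2.5th to the 97.5th percentile.

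**Decision levels.** SAP 5.6 begins "For the primary and secondary endpoints related to safety" and says that alpha "is set to 0.05, to conservatively include all potential safety signals", with no sidedness. For the non-safety secondaries the same section does give it: "the family-wide type I error rate will be controlled at one-sided" 0.025.

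**The concern.** SAP 5.6 is the only analysis section that attaches a significance level to the word primary, and its level is numerically twice the design alpha. Every tested hypothesis under that sentence is directional: the primary in 5.3 and the ten safety secondaries in 5.4.1 to 5.4.6 and 5.4.8 to 5.4.11. A p-value computed as those hypotheses are written is one-sided, and comparing it with 0.05 gives a more lenient test than the one the trial was sized for. Two features of 5.6 keep that reading open. It writes one-sided for the other family and leaves this alpha bare, and it justifies 0.05 as the inclusive choice for safety signals, a rationale that does not suit a confirmatory superiority test.

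The primary verdict is at stake when the one-sided p falls between 0.025 and 0.05. It would be a success under one reading and a failure under the other, and the 95% win-ratio interval would be expected to include 1. The trial is open-label, so the threshold should not be left to interpretation after data are seen. For the safety secondaries, the label decides whether small differences in rare events are called significant.

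**Working it through.** **The plan's own figure.** The 432 comes from a simulation whose component proportions are not in either document, so it cannot be rebuilt. What follows uses only the stated alpha, power and N, with a normal approximation.

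**1. Critical values.**
- One-sided 0.025: z = 1.960
- Two-sided 0.05: z = 1.960
- One-sided 0.05: z = 1.645

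The first two are the same test in FlowTriever's favour. The third has 5% type I error.

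**2. Check on the F-S statistic itself.** The statistic was simulated under no effect at 216 per arm, with 20,000 replicates. Assumed rates in both arms were death 2%, ICH 1%, major bleeding 6%, deterioration or bailout 6%, and ICU categories 30/20/50%. Rejection in favour of FlowTriever was 4.95% at one-sided 0.05 and 2.49% at one-sided 0.025 (or two-sided 0.05). The normal approximation is adequate.

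**3. How often the two readings disagree on the primary.** This is P(1.645 < Z < 1.960) with Z ~ N(θ, 1). The design effect at N = 432 is θ = 1.960 + 0.842 = 2.802.

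| Situation | θ | Success at 1.645 | Success at 1.960 | Disagree |
|---|---|---|---|---|
| No effect | 0 | 5.0% | 2.5% | 2.5% |
| Design effect, 432 analysed | 2.802 | 87.6% | 80.0% | 7.6% |
| Design effect, 550 analysed | 2.802 × √(550/432) = 3.161 | 93.5% | 88.5% | 5.0% |
| Worst case | 1.802 | 56.3% | 43.7% | 12.5% |

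If 0.05 is two-sided, the last column is zero throughout.

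**4. Safety secondaries.** Fisher's exact test, 275 per arm. The counts are illustrative assumptions, chosen to show where the label matters.

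| FlowTriever vs CDT | One-sided p | Two-sided p | Does the label change the verdict at 0.05? |
|---|---|---|---|
| 0 vs 5 (e.g. ICH) | 0.031 | 0.061 | Yes |
| 5 vs 13 (e.g. major bleeding) | 0.045 | 0.091 | Yes |
| 0 vs 6 | 0.015 | 0.030 | No |

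**5. The simulation sentence.** Power at one-sided 0.025 with N analysed is Φ(k × √(N/432) − 1.960). Here k = 1.960 + 0.842 = 2.802 if the program counted two-sided p ≤ 0.05 (or one-sided p ≤ 0.025), and k = 1.645 + 0.842 = 2.486 if it counted one-sided p ≤ 0.05.

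| N analysed | k = 2.802 | k = 2.486 |
|---|---|---|
| 432 | 80.0% | 70.1% |
| 500 | 85.4% | 76.3% |
| 550 | 88.5% | 80.1% |

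Nothing in the documents shows that the second column applies.

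**The case against.** The strongest case against is that 5.6 states no sidedness, so z 1.645 is not its literal content; the reader has to bring one-sided over from 5.3. Two-sided is the better-supported inference. Both simulation paragraphs give one-sided 2.5% and then count p-values up to 0.05, and these statements agree only if the p-values are two-sided. The 2.5th and 97.5th percentile limits of the win-ratio interval also correspond to z 1.960. This stands. It makes the two-sided reading the likelier one, but no sentence says so.

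A second objection is that the phrase about safety may qualify primary as well as secondary. Protocol section 9 lists a safety-related primary endpoint made up of four components, without ICU stay. On that reading 5.6 does not govern the five-component test, and the design alpha of one-sided 2.5% is the only level given for it. That is also possible. It removes the conflict for the primary but leaves SAP 5.3 and 5.6 without a decision level for it.

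Third, the safety counts in the working are invented, and 5.6 uses 0.05 there as an unadjusted screen for signals. That is fair: these results would not decide the trial, and the counts show only that the label can matter.

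A reader might go further and infer that the primary will be tested at twice its design alpha, or that the trial is underpowered at 70.1%. The documents support neither. The first depends on the less favoured reading of 5.6. The second depends on a counting rule that there is no evidence was used, and under which the simulation paragraph would contradict its own opening.

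**Conclusion.** The point holds as an unresolved ambiguity in the decision rule, not as a proven error. It should be fixed because the less favoured reading doubles the type I error of the primary and can turn a failed primary into a success, while removing the doubt takes a few words. The primary verdict is affected only if 0.05 is applied to the one-sided p-value and that p lies between 0.025 and 0.05. The disagreement probabilities rest on the normal approximation and, for the design effect, on 432 giving 80% power at one-sided 2.5% as stated. The simulation wording affects only how planned power is described.

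**What to change.** Before database lock:

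- **SAP 5.3 and 5.6:** state that the primary F-S test is judged at one-sided alpha 0.025 (equivalently two-sided 0.05), and take the primary out of the unlabelled 0.05 sentence.
- **SAP 5.6:** label the 0.05 kept for the safety secondaries as one- or two-sided. The ten hypotheses need no rewriting once this is done.
- **SAP 5.2:** after checking the simulation program, state the power count as two-sided p ≤ 0.05 (equivalently one-sided p ≤ 0.025). Restate the power only if the program counted one-sided p ≤ 0.05.
- **Protocol section 10:** correct the same sentence at the next amendment. It does not justify an amendment of its own, since each amendment needs IRB/EC approval.

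The cost is a few words in the SAP and one look at the program. There are two downsides. If the safety 0.05 is labelled two-sided, borderline differences in rare events, such as 0 vs 5, would not be called significant. If the program did count one-sided p ≤ 0.05, the restated power would be less favourable.
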